## The ShortCut™ Continued Access Study (CAS) Protocol Synopsis

### **1 Full title**

A Prospective, Multicenter, Non-Randomized, Single-Arm, Open-Label Continued Access Study of the ShortCut™ device (The ShortCut™ CAS).

### **2 Intended Use**

The ShortCut™ is indicated for use as a splitting device of bioprosthetic aortic valve leaflets to facilitate percutaneous valve-in-valve procedures.

### **3 Device name**

ShortCut™

### **4 Design**

This is a prospective, multicenter study sponsored by Pi-Cardia Ltd.

This Continued Access Protocol has been written to allow ongoing treatment of patients at selected investigational sites while the marketing application for the ShortCut™ device is under review.

### **5 Objective**

The continued access phase will be used to collect additional safety and effectiveness data of the ShortCut™ device for splitting bioprosthetic aortic valve leaflets, and to demonstrate coronary artery ostia patency following leaflet split, in patients who are at risk for TAVR-induced coronary artery ostium obstruction following a ViV procedure. The data gathered in this phase will support the objectives and outcomes of the original IDE pivotal study.

### **6 Endpoints**

#### **6.1 Primary Endpoints**

##### **6.1.1 Primary safety endpoint**

Each of the following ShortCut™ device- and/or ShortCut™ procedure-related serious adverse events will be assessed at discharge or at 7 days post-procedure, whichever occurs first:

- Mortality
- Stroke (fatal, disabling and non-disabling)

##### **6.1.2 Primary effectiveness endpoint**

Overall leaflet splitting success using the ShortCut™ device assessed intra-procedurally by echocardiography and or angiography.

Per patient leaflet splitting success will be determined as follows:

- For patients in whom one leaflet was intervened, splitting success per patient will be determined based on the splitting success of the intervened leaflet:
  - Visualization of leaflet split, assessed by intraprocedural TEE immediately post-ShortCut™ procedure and prior to TAVR, OR
  - Increase in aortic regurgitation from pre to post leaflet split, assessed by intraprocedural TEE or angiography.
- For patients in whom two leaflets were intervened, splitting success per patient will be determined based on the splitting success of the first intervened leaflet.

## 6.2 Secondary Endpoints

### 6.2.1 Secondary safety endpoints

The following will be assessed through 30 days post index procedure (according to VARC-3):

- All-cause mortality
- All-cause stroke (fatal, disabling and non-disabling)
- Coronary obstruction
- Myocardial infarction with new evidence of coronary artery obstruction requiring intervention
- Major vascular complications
- Cardiac tamponade
- Acute kidney injury
- Access-related type 3-4 bleeding

### 6.2.2 Secondary effectiveness endpoints

- Per intervened leaflet splitting success will be assessed intra-procedurally and will be determined based on the splitting success of this leaflet:
  - Visualization of leaflet split, assessed by intraprocedural TEE immediately post-ShortCut™ procedure and prior to TAVR, OR
  - Increase in aortic regurgitation from pre to post leaflet split, assessed by intraprocedural TEE or angiography.
- The following endpoints will be assessed through 30 days post index procedure:
  - Freedom from coronary artery ostia obstruction related to the intervened leaflet
  - Freedom from coronary artery intervention related to the intervened leaflet

### 6.2.3 Technical success endpoint

A composite of the following, which will be assessed at exit from procedure room following the ShortCut™ procedure:

- Successful access, delivery, and retrieval of the ShortCut™ device
- Freedom from ShortCut™ device- and/or ShortCut™ procedure-related mortality
- Freedom from ShortCut™ device- and/or ShortCut™ procedure-related:
  - Surgery or intervention
  - Major vascular or access-related complications
  - Cardiac structural complication

### 6.3 Tertiary Safety Endpoints

The following will be assessed through 90 days post index procedure (according to VARC-3):

- All-cause mortality
- Stroke
- Myocardial infarction with new evidence of coronary artery obstruction requiring intervention

## 7 Patient population

Patient population will include patient who are planned to undergo a percutaneous valve-in-valve (ViV) procedure for an approved ViV indication, and who are at risk for TAVR-induced coronary artery ostium obstruction, according to the local Heart Team decision. Continued Access studies are approved by FDA on a time-limited phased basis, therefore sample size in this study will be based upon FDA-approved limits. The first enrollment phase will include up to 24 patients for whom the ShortCut™ procedure was initiated (up to 30 enrolled). Following this and subject to FDA approval, expansion of the study for the inclusion of up to 20 additional enrolled patients according to time limits agreed with the FDA.

## 8 Eligibility Criteria

### 8.1 Main Inclusion criteria

1. Male or female ≥ 18 years of age at the time of screening.
2. Patient is planned to undergo a percutaneous valve-in-valve procedure for an approved ViV indication due to a failed bioprosthetic valve.
3. Patient is at risk for TAVR-induced coronary artery ostium obstruction.

## 8.2 Main Exclusion criteria

1. An excessive aortic valve leaflet Calcium morphology, such as diffuse massive calcification at the targeted leaflet for splitting or anatomy not suitable for the use of the ShortCut™device, as determined by the CT measurements.
2. Leaflet planned to be intervened is torn pre-ShortCut device access.
3. Patient has iliofemoral vessel characteristics that preclude safe insertion of the introducer sheath.
4. Planned concurrent intervention in the same setting of the index procedure.
5. Surgery or interventional procedure ≤ 1 month prior to the index procedure.
6. Planned provisional (pre-position coronary artery) stents.
7. Coronary disease that, in the opinion of the local Heart Team, should be treated; or treatment of coronary disease ≤ 1 month prior to index procedure.
8. Carotid or vertebral artery disease that, in the opinion of the local Heart Team, should be treated; or treatment of carotid stenosis ≤ 1 month prior to index procedure.
9. CVA or TIA ≤ 6 months prior to index procedure.
10. Severe neurological disability, as determined by the Investigator.

## 9 Study schedule and time points

### *Study requirements from baseline through follow-up*

	Screening 60 days prior to procedure	Baseline 7 days prior to procedure	Index procedure	Pre-discharge	30 days post- procedure	90 days post- procedure 
Informed consent	X					
Medical and surgical history review	X					
NYHA classification	X				X	
Risk assessment, including EuroSCORE II and STS score	X					
Physical examination		X			X	
Blood tests 	X 	X 		X		
12-lead ECG	X	X 		X	X	
Modified Rankin Score and NIHSS 		X		X 	X 	
CT of heart, aortic root, and aortic arch	X 					
Echocardiographic imaging	X 		X 			
Invasive or CT coronary angiography	X 					
ShortCut™ assisted TAVR			X			
Angiography for coronary patency			X			
Adverse events recording		X	X	X	X	X
Medications recording	X	X	X 	X 	X 	X 
Clinical status remote evaluation						X

 The relevant blood assays and exact timepoints, are listed above under each visit section.

 CT scan will be performed only in case no adequate CT scan was performed within 6 months prior to screening.

 TTE at screening will be performed only in case no adequate TTE was performed within 90 days prior to screening.

 Invasive or CT coronary angiography will be performed only in case no invasive or CT coronary angiography was performed within 1 year prior to screening, or the patient had new ischemic symptoms since last invasive or CT coronary angiography.

 Review medications and record only if there is a change from previous visit (e.g. due to change in health condition or as a result of an adverse event)

 Intra-procedure TEE will be performed during the ShortCut™ procedure.

 Modified Ranking Score and NIHSS assessments shall be done only for patients who had a suspected neurological event.

 In the event a patient experiences a stroke event within 30 days post index procedure, an additional visit at 90 days after the onset of event will be performed and will include Modified Ranking Score and NIHSS assessments.

 ECG at baseline will be performed only in case no ECG was performed within 30 days of procedure.

## 10 Statistical Analysis Plan

### 10.1 Study Analysis Sets

#### 10.1.1 Safety analysis set

The safety analysis set will include all patients who reached the point of index procedure, i.e., patients in whom the ShortCut device was introduced through the introducer sheath. Patients who were treated with the ShortCut without meeting the eligibility criteria will also be included in this analysis set.

#### 10.1.2 Primary effectiveness analysis set

The primary effectiveness analysis set will include the Evaluable Patients – patients in whom split with the ShortCut device was attempted, and were determined to have Adequate Imaging to visualize split or demonstrate increase in AR according to the echo or angiography core lab.

Echocardiography imaging is considered Adequate if either visualization of split or increase in AR can be assessed. Angiography imaging is considered Adequate if increase in AR can be assessed.

#### 10.1.3 Secondary effectiveness analysis set

The secondary effectiveness analysis set will include patients in whom the following ShortCut procedure steps have been performed: access, delivery to the aortic valve, activation of the ShortCut Splitting Element and split attempt.

All intervened leaflets of these patients will be included in the secondary effectiveness analysis set.

#### 10.1.4 Per Protocol (PP) analysis sets

##### 10.1.4.1 Per Protocol Primary Effectiveness (PPPE) analysis set

The PPPE analysis set will include patients who are included in the primary effectiveness analysis set and who do not have major protocol violations that are likely to affect the study primary endpoints (effectiveness or safety).

##### 10.1.4.2 Per Protocol Secondary Effectiveness (PPSE) analysis set

The PPSE analysis set will include patients who are included in the secondary effectiveness analysis set and who do not have major protocol violations that are likely to affect the study primary endpoints (effectiveness or safety).

### 10.2 Sample Size Considerations

The data gathered in this continued access phase will support the objectives and outcomes of the original IDE pivotal study. Therefore, the study endpoints will not be statistically powered. The analysis for the efficacy and safety of the Shortcut™ device will follow a designated statistical analysis plan. Continued Access studies are approved by FDA on a time-limited phased basis, therefore sample size in this study will be based upon FDA-approved limits. The first enrollment study phase will include up to 30 enrolled patients:

- Up to 24 patients for whom the ShortCut™ procedure was initiated and either the following occurred:

- Split was attempted and were determined to have adequate Imaging
- Split was not attempted for any reason, or
- Split was attempted but were determined to have Inadequate Imaging
- Up to 6 additional enrolled patients who dropped out from the study prior to the index procedure (before the ShortCut™ procedure was initiated), due to: death, consent withdrawal by patient or by physician, patient lost to follow up, or other reasons).

Following this phase and subject to FDA's approval, expansion of the study for the inclusion of up to 20 additional enrolled patients according to time-limited phased basis agreed with the FDA.

The population flowchart is provided below:

[figure not shown]

Figure 1: Study population flowchart

### 10.3 Use of Controls

In this clinical study, there is no control group, no use of blinding techniques and no randomization distribution system.

## **10.4 Statistical Analyses**

### **10.4.1 Overview**

The data will be summarized in tables listing the mean, standard deviation, median, minimum, maximum and number of patients for continuous data, or in tables listing count (frequency) and percentage for categorical data.

All statistical analyses will be performed, and data appendices will be created, using the SAS® or Stata system. The effects of noncompliance, dropouts and possible covariates will be assessed to determine the impact on the general applicability of results from this study; however, no imputation for missing data will be performed.

The results will be presented descriptively or in listings.

### **10.4.2 Patient disposition**

Patient disposition will be tabulated; the number of enrolled, treated, prematurely terminated and completed patients will be summarized. Baseline demographics and characteristics will be summarized at the level of patient.

A list of dropouts will be prepared including reason for discontinuation and time of discontinuation.

### **10.4.3 Primary safety analysis**

The primary safety analysis will be performed on the safety analysis set.

Frequency distribution of patients with ShortCut device and/or ShortCut procedure related mortality and/or stroke events, as determined by the CEC, and assessed at discharge or at 7 days post-procedure, whichever occurs first, will be presented, along with the 95% confidence intervals.

### **10.4.4 Secondary safety analysis**

The secondary safety analysis will be performed on the safety analysis set.

Frequency distribution of all AEs will be presented by body system and preferred term, severity and relation to ShortCut device and/or ShortCut procedure, as determined by the CEC. For each AE of interest, the tabulation will include the number of AEs and the number and percentage of patients experiencing it.

### **10.4.5 Tertiary safety analysis**

The tertiary safety analysis will be performed on the safety analysis set.

Frequency distribution of all AEs will be presented by body system and preferred term, severity and relation to ShortCut device and/or ShortCut procedure, as determined by the CEC. For each AE of interest, the tabulation will include the number of AEs, the number and percentage of patients experiencing it.

### **10.4.6 Additional safety analyses**

Survival analysis of time to all-cause mortality and time to first stroke will be done using Kaplan-Meier curve. Estimates of all-cause mortality and stroke rates at day 30 and day 90 will be estimated based on the Kaplan-Meier curve.

All AEs and SAEs obtained throughout the 90 days of follow up will be coded and presented by body system, preferred term, severity and relation to the device and/ or procedure. AEs will be presented separately for the first month post-procedure, and the subsequent two months.

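### The day-30 and day-90 stroke rates in 10.4.6 come from a Kaplan-Meier curve with no competing-event treatment of death; a cumulative incidence estimate would match the label better, though the difference is small

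*Combined protocol and SAP*

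**What the plan says.** Section 10.4.6 (Additional safety analyses) gives one method for two outcomes: "Survival analysis of time to all-cause mortality and time to first stroke will be done using Kaplan-Meier curve". It then says what is read from the curves: "Estimates of all-cause mortality and stroke rates at day 30 and day 90 will be estimated based on the Kaplan-Meier curve". It gives no censoring rule, does not say how a death without stroke is handled, and names no competing-risk method.

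Other sections bear on the point:

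- Stroke is a named endpoint through 30 days (6.2.1) and through 90 days (6.3). Section 6.2.1 counts fatal stroke as stroke; 6.3 lists stroke without spelling this out.
- Crude figures on the safety set are planned as well. For each adverse event of interest, 10.4.5 states that "the tabulation will include the number of AEs, the number and percentage of patients experiencing it", and 10.4.4 has a near-identical sentence.
- The first phase treats up to 24 patients. Section 7 allows, subject to FDA approval, "expansion of the study for the inclusion of up to 20 additional enrolled patients".
- Section 10.2 states: "Therefore, the study endpoints will not be statistically powered". Section 10.4.1 makes the presentation descriptive.

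**The concern.** A patient who dies without a stroke can no longer have one, so death is a competing event for stroke. A standard Kaplan-Meier curve for time to first stroke censors that patient, as if the risk of stroke continued unobserved. One minus the curve then describes a hypothetical population in which nobody dies. A reader of a day-90 stroke rate will take it as the share of treated patients who had a stroke by day 90, which is a different quantity. All-cause mortality has no such problem.

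What is at stake is whether the rate means what its label says, and whether it agrees with the plan's own tables. With complete follow-up, the cumulative incidence equals the crude percentage exactly. The Kaplan-Meier figure departs from it once a stroke-free death precedes a stroke, so the same patients can yield two different stroke percentages with nobody lost to follow-up.

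**Working it through.** The documents state no stroke rate, death rate or event count, so there is no figure of the plan's to reproduce. The check compares the two estimators.

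**Inputs from the documents.** n = 24 treated (section 7). An upper bound of 24 + 20 = 44 after expansion; it is a bound because the 20 are enrolled, not necessarily treated. Reporting days 30 and 90 (10.4.6).

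**Assumptions.** Stroke-free deaths are censored (usual convention, not stated). Fatal strokes count as stroke events, as in 6.2.1, so only stroke-free deaths compete. Nobody is lost before day 90. 90-day death is 2% to 15% and stroke 2% to 10%.

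**Formulas.** With r patients still at risk just before each stroke:

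- One minus Kaplan-Meier = 1 − product over strokes of (1 − 1/r).
- Aalen-Johansen cumulative incidence = sum over strokes of S × (1/r), where S is the proportion alive and stroke-free just before that stroke.

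**Worked cases, n = 24.**

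- One death, then one stroke: 1/23 = 4.35% against (23/24)(1/23) = 1/24 = 4.17%. Gap 0.18 points.
- Two deaths, then one stroke: 1/22 = 4.55% against 1/24 = 4.17%. Gap 0.38 points.
- Three deaths, then two strokes: 1 − (20/21)(19/20) = 2/21 = 9.52% against (21/24)(1/21) + (20/24)(1/20) = 2/24 = 8.33%. Gap 1.19 points.
- One stroke before any death: 1/24 by both. Two strokes and no deaths: 2/24 by both. Gap 0.

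At n = 44 the first three patterns give 1/43 against 1/44, 1/42 against 1/44, and 2/41 against 2/44: gaps of 0.05, 0.11 and 0.33 points.

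**Expected gap at day 90 under constant hazards.** Let hs = −ln(1 − s) and hd = −ln(1 − d) for assumed 90-day stroke s and death d. One minus Kaplan-Meier targets s. The cumulative incidence is hs/(hs + hd) × [1 − (1 − s)(1 − d)].

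- d = 2%, s = 2%: 0.5 × (1 − 0.9604) = 1.98% against 2%. Excess 0.02 points.
- d = 5%, s = 5%: 0.5 × (1 − 0.9025) = 4.88% against 5%. Excess 0.12 points.
- d = 15%, s = 10%: hs = 0.1054, hd = 0.1625; 0.3933 × (1 − 0.765) = 9.24% against 10%. Excess 0.76 points.

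**Day 30.** In the last scenario, with each cumulative hazard cut to a third, one minus Kaplan-Meier is 1 − 0.9^(1/3) = 3.45% and the cumulative incidence is 0.3933 × (1 − 0.765^(1/3)) = 3.36%, an excess of 0.09 points. Events clustered soon after the procedure would move this figure towards the day-90 one.

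**Spread across trials.** Simulating 20,000 trials per scenario under the same constant hazards, at day 90:

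| n | Death, stroke | Trials where the estimates differ | Mean excess (points) | 95th percentile (points) |
|---|---|---|---|---|
| 24 | 2%, 2% | 8% | 0.02 | 0.18 |
| 24 | 5%, 5% | 34% | 0.13 | 0.60 |
| 24 | 10%, 10% | 68% | 0.50 | 1.67 |
| 44 | 2%, 2% | 21% | 0.02 | 0.11 |
| 44 | 5%, 5% | 64% | 0.12 | 0.44 |
| 44 | 10%, 10% | 93% | 0.50 | 1.32 |

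**Scale of sampling error.** The Clopper-Pearson 95% interval is 0.1% to 21.1% for 1 stroke in 24, and 1.0% to 27.0% for 2 in 24.

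**The case against.** The case for leaving the plan alone has three parts.

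First, the plan never says that deaths are censored. That is correct. Censoring is the default when only Kaplan-Meier is named, but it remains an inference. If stroke-free deaths were instead kept in the risk set to day 90, the curve would return the crude share and there would be no gap. The plan should say which applies.

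Second, the better number is largely reported already, because with complete follow-up the cumulative incidence is the crude percentage. This largely stands. Adverse event of interest is not defined, but a named endpoint such as stroke is its natural reading. The tables do not remove the point, though: they put a second stroke percentage beside the curve-based one, and in the third worked case the pair would read 8.3% and 9.5%. If patients are lost before day 90, the cumulative incidence also uses their partial follow-up, which a crude percentage does not.

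Third, nothing depends on it. This stands in full. These are additional descriptive analyses in an unpowered study, and the primary safety analysis (10.4.3) is a frequency with a confidence interval, not a survival curve.

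A reader might infer that the planned method overstates stroke in every data set, or by a point or so as a rule. The documents do not support that. The gap is zero unless a stroke-free death precedes a stroke by the reporting day, and the 1.19-point case places all three deaths before both strokes, the least favourable order for those counts.

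**Conclusion.** A minor point that holds. As written, 10.4.6 takes stroke rates from Kaplan-Meier without treating death as a competing event. Under the usual convention the result can equal or exceed the cumulative incidence of stroke but never fall below it. The expected excess at day 90 is about 0.02 to 0.76 points over the assumed 2% to 15% death and 2% to 10% stroke; individual data sets of 24 can show nothing or more than a point. The size rests on those assumed rates, on constant hazards, and on fatal strokes being counted as events at both time points.

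The excess is far inside the sampling error, and any error makes the device look worse rather than better. It would be wrong to conclude that the safety findings are unreliable or that a decision would change. The reason to act is that in a descriptive study the estimate is the product, and here it can disagree with the plan's own tables when an estimator that uses the same data would not.

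**What to change.** In 10.4.6, keep Kaplan-Meier for all-cause mortality. For time to first stroke, report the Aalen-Johansen cumulative incidence at days 30 and 90, with death without prior or fatal stroke as the competing event, so that the handling of such deaths is stated.

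Section 10.2 says these data are to support the pivotal study, but the documents do not give that study's method. If its stroke rates are Kaplan-Meier and a side-by-side reading is wanted, show both estimates, each labelled.

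The cost is about one sentence in the SAP and minor programming. No extra patients, data or alpha are needed.

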#### **10.4.7 Primary effectiveness analysis**

The primary effectiveness analysis will be performed on the primary effectiveness analysis set. Frequency distribution of Evaluable Patients with a successful split will be presented along with the Clopper-Pearson 95% confidence interval.

#### **10.4.8 Secondary effectiveness analysis**

The secondary effectiveness analysis will be performed on the secondary effectiveness analysis set.

##### **Per Intervened Leaflet Splitting Success**

The secondary effectiveness analysis will present the rate of successful splits along with the Clopper-Pearson 95% confidence interval.

The overall rate of successful splits will also be estimated via generalized estimating equations (GEE, SAS PROC GENMOD) that account for potential dependency between the two leaflets outcomes of the same patient.

